12.0 RISKS and BENEFITS

12.1 RESEARCH-RELATED RISKS: Check if your study involves any of these specific research-related risks to participants that may need to be disclosed in the consent form:

For interventional studies, risk that the regimen may be more harmful or less effective than other available interventions

- Risks associated with radiation exposure for imaging studies specifically for research purposes
- Risks associated with the administration of contrast agent for imaging studies
- Risks associated with withholding of treatment or discontinuation of current treatment (e.g., washout period is required by the study protocol)
- For randomized, placebo-controlled trials, possible temporary or permanent health consequences from the deprivation of effective therapies during the placebo administration period
- For studies involving a sham surgical procedure, the risk that participants may experience increased morbidity without the possibility of benefit
- Risks associated with modification or extension of a surgical procedure primarily for research purposes (e.g. risks associated with prolonging anesthesia, time in the operating room, etc.)
- Risk of pain or physical discomfort caused by the research intervention
- Possible personal discomfort due to sensitive topics (stress, embarrassment, trauma)

12.2 RISKS: Describe any anticipated risks and discomforts not listed above:

There are no more than minimal medical or psychological risks associated with this research.

tDCS. Commonly observed adverse effects of tDCS are that skin irritation may occur at the site of the tDCS electrodes. tDCS may also cause minor adverse effects such as headache.

Pupillometry. Pupillometry is a minimal risk procedure and entail wearing eye glasses and potential discomfort of wearing the eyeglasses can occur with this procedure. Every effort will be made to maintain confidentiality, however this cannot be guaranteed.

Anxiety Task. Discomfort may be felt when determining the level of the "buzz" stimulus. We will start with a low level of "buzz" and step up gradually until the patient reports a level 7 for "annoying". The stimulus is meant to be "highly annoying" but not painful. At any time the patient reports pain, we will

decrease the "buzz" stimuli to the patient's level of comfort, as they self-report "annoying" but not "painful" level. The patient may stop at any time or have the stimulus reduced at any time. The number of stimulations delivered will be limited to 10 per 12 minute trial (stimulation associated with either the high or low tone). Parts of the task may become boring or repetitive. Efforts will be made to limit the number of trials administered per visit to minimize subject boredom and discomfort, while ensuring that adequate amounts of data are being collected.

Inhalation of 7.5% CO₂. The primary adverse effect of 7.5% CO₂ inhalation is the induction of Acute Fear which is also the reason that it is being carried out in this study. The fear is generally well-tolerated and resolves within roughly 10 minutes of the end of inhalation. A small percentage of subjects report increased sweating, tremor, tension, and tight muscles during or shortly after inhalation which is generally well tolerated. A gradual rise in blood pressure and pulse with a final systolic blood pressure rise of approximately 18 points, diastolic blood pressure rise of approximately 3 points, and heart rate elevation of approximately 8 points occurs with CO₂ gas as compared to when subjects received "air" inhalation. In rare circumstances severe anxiety could be elicited. There is no evidence that repeated inhalations increases the risks of severe anxiety in response to inhalation testing or in the year following the inhalations. Several studies have evaluated the effects of repeated inhalations with 7.5% CO₂ and higher percentages of CO₂ and not found evidence that there is an increase in fear elicited or an increase in adverse effects with repeated exposures (Poma et al., 2005; Verburg et al., 1998). In addition, a group of healthy non-anxious subjects undergoing repeated exposure to 20% CO₂ inhalation (N=155) were followed for up to a year and compared to a group of healthy non-anxious control subjects who breathed room air (N=56) and there was no evidence that the exposures to 20% CO₂ increased the risk for anxiety /panic during the year of follow-up (Prenoveau et al., 2006).

ECG. Skin irritation from the ECG electrode pads or pain when removing the pads is a possible risk.

12.3

MINIMIZING RISKS: Describe the steps you have taken to minimize the risks/discomforts to subjects. Examples include:

- **designing the study to make use of procedures involving less risk when appropriate minimizing study procedures by taking advantage of clinical procedures conducted on the**
- **study participants**
- **mitigating risks by planning special monitoring or conducting supportive interventions for**
- **the study having a plan for evaluation and possible referral of subjects who report suicidal ideation**

This investigation has been designed to minimize the risks and discomfort incurred by study participants. Efforts will be made to reduce inconvenience to participants by scheduling assessment and experimental sessions at times that are most convenient to them. There will be no inclusion of vulnerable populations in this project (e.g., no children; mentally impaired persons; prisoners). To protect women of reproductive potential from risk, pregnant women, women who are breast feeding, or those who plan to become pregnant during the study will be excluded from study enrollment. For women of childbearing potential, a urine pregnancy test will be conducted, and must be negative before their entry into this study. If sexually active, women must agree to use appropriate contraceptive measures for the duration of the study. Medically acceptable contraceptives include: (1) surgical sterilization, (2) approved hormonal contraceptives (such as birth control pills, Depo-Provera, or Lupron Depot) in combination with a barrier method, (3) barrier methods (such as a condom or diaphragm) used with a spermicide, or (4) an intrauterine device (IUD). Women participants will be instructed to inform their study doctor immediately if they become pregnant during the study at which point participation in the study will end. The study doctor will then track the pregnancy and report the outcome to the Institutional Review Board (IRB). Adverse events will be monitored at each experimental session and standard procedures will be followed whenever an adverse event is recorded. In the event that a participant finds the screening interviews and questionnaires disturbing, the PI will be available to speak with the participant. The Study Coordinators will be trained by the site PI to handle personal material with confidentiality and sensitivity.

tDCS. Multiple steps will be taken to decrease the risks of tDCS. This includes using an electrical dose titration procedure with ongoing adverse event assessment and subject self-rating of discomfort which will guide whether dose increases occur in order to minimize discomfort and risk. This will also allow us to meet a goal of administering a dosage that is the minimum electrical dosage that engages our target to minimize risk. Also, because the

risks of tDCS which we propose to administer are not well characterized we plan to administer treatment for relatively brief periods (up to 10 minute stimulation sessions) and not administer treatments that have an impact on our target neural circuitry as indicated by pupillometry more frequently than weekly. Further, we may monitor ECG and breathing throughout and after all tDCS treatments to further minimize risks. Subjects will also be instructed to indicate if they have pain or discomfort and treatment will be stopped immediately if requested by a subject. Also, electrode sites will be checked for any skin abrasions prior to each treatment, as the presence of these increases the risk of skin burns. Treatment is not given if there are skin abrasions at the electrode sites. We will also carefully monitor subjects for adverse events after every stimulation with the SAFTEE tool and specifically ask them about the presence of the following side effects: itchiness, dizziness, lightheadedness, blurred vision, or headache. If any of these are answered positively, the duration of the symptom/s will be monitored and if it does not dissipate within an hour, which is typical of the symptom/s will be monitored and if it does not dissipate within an hour, which is typical of tDCS, the participant will be assessed by a medical practitioner and appropriate care provided.

Pupillometry. In order to minimize risks of pupillometry, sessions will be kept as short as possible and there will be a study physician with all subjects during the procedure. Subjects will be assessed for adverse events and if they are detected, appropriate care will be made available.

7.5% CO₂ Administration. In order to minimize risks of CO₂ during each 20-min inhalation period, ECG monitoring and recording will occur continuously using a 12-lead ECG (Mortara Instruments) and breathing will be carefully monitored and recorded using pneumotachograph/integrator and data acquisition systems (Hans Rudolph). Skin conductance measures and breathby-breath changes in %CO₂ will be monitored continuously and recorded using a CO₂ sensor connected to a data acquisition system (Hans Rudolph, SmartLab unit). Further, two members of the study team including 1 study physician will remain with the participant constantly during inhalations as a safety measure. Participants will be able to terminate the inhalations at any point and will remain in the testing room until a study physician determines that it is appropriate for them to leave based on an examination. If adverse events are detected, appropriate care will be made available.

Anxiety Task. Efforts will be made to limit the number of trials administered per visit to minimize subject boredom and discomfort, while ensuring that adequate amounts of data are being collected. The subjects will be allowed rest periods between trials to minimize fatigue, they may also elect to terminate testing at any time. Comfort level for the irritating stimulus is determined prior to testing and set for each individual at their own comfort level. Before the anxiety task begins, the level of "annoying buzz" will be determined for the subject based on their verbal responses. First, a low level "buzz" (set at 5V) will be presented through stimulation generated to the ring and pinky fingers of the subject, using the BIOPAC STM-200 Stimulator (duration of less than 0.5 seconds) by the researchers. The subject will be asked to report on a scale of 0 (not at all annoying) to 10 (extremely annoying), how the stimulus feels. The presentation of the "buzz" will increase in increments of 5-10V (with a maximum of 100V) until the subject reports a level 7 for annoying. The purpose of this "annoying buzz" is to be highly annoying, but not to provoke pain. When the subject states the stimulus feels at a level "7" for highly annoying, the "buzz" settings will be set at this voltage.

Protection of Confidentiality will be accomplished by assigning each participant a distinct research code number and using this code number rather than the person's name on all documents and electronic data acquired from that individual. Data acquired from all participants will be kept in locked files at the study site and only this project's staff will have access to these files. When data are analyzed the data sets will include only participants' research code numbers as identifiers. No names or other unique identifiers will be included in any of the data sets used in the planned analyses of this project.

12.4 RESOURCES: Describe the resources in place to conduct this study in a way that assures protection of the rights and welfare of participants: These resources typically include appropriately trained and qualified personnel (in terms availability, number, expertise and experience), funding, space, equipment, and time to devote to study activities. Depending on the nature of the research study, investigators should consider the proximity or availability of critical resources that may be essential to the safety and welfare of participants, such as

the proximity of an emergency facility for care of participant injury availability of psychological support after participation resources for participant communication, such as language translation services

Resources in place to conduct this study in a way that assures the protection of the rights and welfare of participants include:

- 1) all personnel involved in the study, which include the PI, Study Coordinators and Study Clinicians will all be appropriately trained and qualified. The PI has extensive experience as a PI of clinical research studies including studies involving tDCS and other brain stimulation modalities. He also has extensive experience training Study Physicians and Project Coordinators who have safely and effectively completed research projects;
- 2) Adequate funding from NIMH is available for completion of the study
- 3) Sufficient space for the successful completion of the study is available for carrying out the study at Langley Porter Psychiatric Institute
- 4) The necessary equipment is available for successful completion of the study
- 5) The PI, Study Coordinator, and Study Clinicians have the time available to successfully complete this study

12.5 * BENEFITS: (REQUIRED) Note: These are the benefits that the IRB will consider during their review.

They are not necessarily appropriate to include in the consent form.

Possible immediate and/or direct benefits to participants and society at large (check all that apply):

- Positive health outcome (e.g. improvement of condition, relief of pain, increased mobility, etc.)
- Closer follow-up than standard care may lead to improved outcomes or patient engagement
- Health and lifestyle changes may occur as a result of participation
- Knowledge may be gained about their health and health conditions
- Feeling of contribution to knowledge in the health or social sciences field
- The research presents a reasonable opportunity to further the understanding, prevention, or alleviation of a serious problem affecting the health or welfare of children
- Other benefit (describe below)
- None

12.6 RISK TO BENEFIT RATIO: Explain why the risks to subjects are reasonable in relation to anticipated benefits, if any, to the participant or society:

Acute fear occurs with many of the anxiety disorders when affected patients are exposed (including imagining or remembering) to fear evocative stimuli, such as to the object of their phobia, a trauma reminder etc. Although epidemiologic data do not exist specifically for Acute Fear, it can be assumed that it is an extremely widespread problem as anxiety-related disorders are the most prevalent class of psychiatric conditions, affecting approximately 18% of adults. Despite the existence of non-medication therapies and pharmacotherapy for addressing this problem many individuals fail to respond to treatment. Further, no treatments exist that have been developed specifically to address Acute

Fear. Accomplishing the aims of this proposal will advance our understanding of the mechanisms of Acute Fear and represents a step towards developing a treatment specifically for this common condition which has the potential to improve the lives of many individuals who suffer from this type of difficulty. These benefits to society outweigh the risks of the study outlined in the previous sections and taking into account the steps being taken to minimize those risks.

13.0

Data and Safety Monitoring Plan

13.2 * DATA AND SAFETY MONITORING PLAN: (REQUIRED)

All greater than minimal risk studies are required to provide a plan. Lack of an adequate plan is one of the most common reasons why IRB approval is delayed.

Instructions:

Describe the plan for monitoring data quality and participant safety. Key areas that should be included in the plan are:

- An explanation of the plan to monitor data collection, study progress, and safety
- A description of who will perform the monitoring and at what frequency (e.g., the PI only, a contract research organization, a Data and Safety Monitoring Board or Data Monitoring Committee, etc.)
- The type of data and events that will be reviewed (e.g., adverse events, breaches of confidentiality, unanticipated problems involving risk to participants or others, unblinded efficacy data, etc.)
- Procedures and timeline for communicating monitoring results to the UCSF IRB, the study sponsor, and other appropriate entities
- Assurance that the research team will adhere to the **UCSF IRB reporting requirements**

As appropriate:

- A plan for conducting and reporting interim analysis
- Clearly defined stopping rules
- Clearly defined rules for withdrawing participants from study interventions

Because of the novel nature of the proposed work and that the adverse effects profile of the form of tDCS we propose to study is not well-documented, we have set up a Data and Safety Monitoring Board (DSMB) for both the R21 and R33 phases of the proposed effort. The individuals who serve on the DSMB were chosen in conjunction with NIH Program staff and have extensive experience conducting clinical trials and are highly familiar with the proposed methodology. The DSMB will convene every 6 months to review ongoing study procedures, discuss AEs and other safety issues, and to evaluate ongoing methods for maintaining data integrity and confidentiality. They will be provided with a summary of all AEs, outcome data, progress data and subject ratings of treatment tolerability prior to each meeting. They will play a critical role in working with the PI and NIH Program to assess whether the "Go-No-Go" criteria are met for proceeding to the R33 phase. If a decision is made to proceed, they will then monitor the R33 study. Should the DSMB members develop any concerns on the basis of information provided to them by the PI, they may request to examine hard or electronic copies of the participants' research records or other information. In transferring information to the DSMB participants' identities will be protected by transferring only data that are de-identified (hard copies) and/or encrypted (electronic data). In considering the frequency of meetings, we have tried to strike a proper balance between maintaining participant safety and the integrity of the study, and the consequent time and workload. Traditionally, DSMBs convene once a year. However, given the novel nature of this trial and that the risks of the form of tDCS we are administering are not well documented it was felt that every 6 month meetings were appropriate. After each meeting the DSMB will compile the information gained from the monitoring activities and subsequently prepare a report summarizing findings. Also included in the report is their recommendation to continue or discontinue the study. This report is completed and delivered to the NIH and the PI. If the DSMB concludes that the study should be terminated, this opinion will be conveyed to the UCSF business officials as well in the case of this latter type of recommendation. Subsequently the PIs, appropriate business officials at UCSF, and NIH Program will likely discuss the matter further before a final decision regarding study termination is made.

Local Monitoring of Subjects, Rules for Withdrawing Participants from Study Interventions, and Safety Stopping Rule: All subjects who undergo tDCS treatments will be carefully monitored locally by one of the study physicians. A study physician will be in the room with all subjects when any study procedures are carried out. There will be close monitoring of the tolerability of each of the tDCS electrode configurations studied. In order to determine the tolerability of particular tDCS electrode placement and electrical stimulus intensities, subjects will rate their discomfort immediately after each tDCS stimulus on a 5-point Likert scale that has been widely used to assess the tolerability of procedures including colonoscopy, nasogastric tube insertion, burn dressing application, and orthodontic procedures. The anchors are: 0="No Discomfort", 1="Minimal Discomfort", 2="Mild Discomfort", 3="Moderate Discomfort", and 4="Severe Discomfort". We employ a cutoff of no more 2 as an indicator of acceptable tolerability. We will employ the following stopping rule for each tDCS configuration test: "If any tDCS electrode configuration is rated at 3 or higher by 3 subjects, all testing with that electrode configuration will cease." In addition, if there is an SAE consisting of the development of new neuropsychiatric symptoms, the study will be halted until the cause of the symptoms is ruled not to be due to the study and, if such an event is determined to be related to the study, the study will not be restarted until modifications to the study methods are made that reduce the risk of such an event recurring based on a review and approval by the DSMB. Any subject who rates tolerability as 3 or greater for any electrode configuration will be withdrawn from further participation. Subjects will be informed that, at any time, they may request to the study physician that study procedures stop and this will occur. This includes that they will specifically be told that they should indicate if they would like tDCS stimulation to

stop during stimulation and it will cease and that they should indicate if they would like to stop CO2 inhalation during the CO2 inhalation procedure and that procedure will immediately be terminated.

Plan for Conducting and Reporting Interim Analysis and Stopping Rule

The study structure is such that there will be 4 cohorts of subjects each consisting of 10 subjects. Each of the first 3 cohorts will be stimulated with a different tDCS electrode configuration to determine if we can find one which is tolerable and inhibits locus coeruleus activity (as indicated by inhibition of a pupil dilatory response). After each cohort we will carry out an interim analysis to determine if this was the case (80% had tolerability ratings of 2 or less and there was statistically significant inhibition of the pupillary response to the anxiety task or auditory oddball task). Each of these interim analyses will be reported to the DSMB. If after the 3 cohorts are completed and if none of the 3 tDCS configurations tested meet the success criteria, then the study will cease. If one of the tDCS configurations meets the success criteria then an additional 10 subjects will be run using the successful tDCS configuration and using 7.5% CO2 instead of the anxiety task or auditory oddball test to elicit a pupillary response.

13.3 * DATA AND SAFETY MONITORING BOARD (DSMB): Will a Data and Safety Monitoring Board (DSMB) be established: (REQUIRED)

Yes

No

13.4 DSMB DETAILS: Provide details from the DSMB's charter, including meeting frequency, and affiliations and qualifications of members: If the DSMB has not yet been established, submit these details to us as they become available.

The DSMB will convene every 6 months to review ongoing study procedures, discuss AEs and other safety issues, and to evaluate ongoing methods for maintaining data integrity and confidentiality. They will be provided with a summary of all AEs, outcome data, progress data and subject ratings of treatment tolerability prior to each meeting. In transferring information to the DSMB participants' identities will be protected by transferring only data that are de-identified (hard copies) and/or encrypted (electronic data). After each meeting the DSMB will compile the information gained from the monitoring activities and subsequently prepare a report summarizing findings. Also included in the report is their recommendation to continue or discontinue the study. This report is completed and delivered to the NIH and PI. If the DSMB concludes that the study should be terminated, this opinion will be conveyed to the UCSF business officials as well. In the case of this latter type of recommendation. Subsequently the PIs, appropriate business officials at UCSF, and NIH Program will likely discuss the matter further before a final decision regarding study termination is made. The members of the DSMB are: [name] MD (Chairman), Professor of Psychiatry, Emory University who has extensive experience in carrying out research studies involving BrainStimulation therapies; [name], Professor of Psychiatry University of Iowa who has extensive experience in carrying out studies employing pupillometry in assessing psychiatric disorders; and [name]., Professor of Biostatistics at Wake Forest University who has extensive experience in Biostatistics.

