3. **Anxiety Task:** Using the eye-tracking system to track pupil changes, the subject may undergo the anxiety task which involves two different epochs: high tone and low tone. Before the anxiety task begins, the level of "annoying buzz" will be determined for the subject by the research team, based on the verbal responses from the subject. First, a low level "buzz" (set at 5V) will be presented through stimulation generated to the index and middle fingers of the subject, using the BIOPAC STM-200 Stimulator (duration of less than 0.5 seconds) by the researchers. The subject will be asked to report on a scale of 0 (not at all annoying) to 10 (extremely annoying), how the stimulus feels. The presentation of the "buzz" will increase in increments of 5-10V (with a maximum of 100V) until the subject reports a level 7 for highly annoying. The purpose of this "annoying buzz" is to be highly annoying, but not to provoke pain. Once this level is set, the anxiety task is initiated during which the subject will be seated in a dark room and instructed to focus on crosshairs displayed on a computer monitor. The anxiety task consists of two block types: (1) high tone and (2) low tone. Two tones of different frequencies (high and low) are played for 5 seconds at a time throughout a trial. Each trial lasts 12 minutes and consists of each tone (high and low) played 20 times (totaling to 40 tones at 5 seconds each). Stimulation will be delivered 50% of the time in association with either the high or low tone in a given trial (subject receives stimulation 10 times per trial). At each study visit (up to 3 visits, scheduled one week apart) for subjects 1-30, the subject will complete 4-6 trials during which tDCS will be administered at gradually increasing electrical doses during 50% of the trials. The other 50% of the trials will be administered without tDCS or with sham tDCS to establish the subject's baseline pupil response to the anxiety task. Subjects will be given a 5 minute break between each trial.

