current state with respect to those feelings from 1 (not at all) to 4 (very much so). It will be administered just before and just after CO₂ administration.

5. **Generalized Anxiety Disorder-7 (GAD-7)**. The 7 item questionnaire may be administered at screening visits to identify anxiety state and trait correlations with pupil physiology.
6. **Beck Anxiety Inventory (BAI)**. This questionnaire may be administered at screening visits to identify anxiety state and trait correlations with pupil physiology.
7. **Adverse Effects (AE) Assessment**. The Systematic Assessment for Treatment Emergent Events (SAFTEE) will be used to monitor AEs. It is reliable and valid and used by [name] in prior studies.

Attach any unpublished instruments in the 'Other Study Documents' section of the Initial Review Submission Packet form after completing the study application. Published instruments should NOT be attached.

8.12 * BIOSPECIMEN COLLECTION: Are you drawing any blood or collecting other biosamples (e.g. tissue, buccal swabs, urine, saliva, hair, etc.): (REQUIRED)

Yes No

8.25 STATISTICAL METHODS: Briefly summarize the methods and types of analyses that will be performed:

All dependent measures will be tested for distribution normality and meeting homogeneity of variance requirements for parametric statistics. Data transformations will be conducted where indicated.

1. Primary Hypotheses.

R21. Testing R21 hypotheses equates to testing if the "Go-No-Go" criteria for proceeding to the R33 are met.

1) Hypothesis 2a: We can identify an electrode configuration for active tDCS that is well-tolerated (5-point Likert scale rating mild discomfort) and significantly suppress the Anxiety Task or Auditory Oddball

Task (AOT) pupil dilation response in 8/10 subjects in the 3rd round of treatment optimization. The Anxiety Task or AOT response will be determined using a repeated measures analysis of variance * (RMANOVA) with condition (common vs rare) as the independent measure and pupil diameter as the dependent repeated measure. If there is a statistically significant difference between the two conditions during treatment it will be assumed that suppression did not occur.

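### Anxiety Task trials run at a lowered buzz, or cut short, have no scoring rule, so they can be counted as tDCS suppression when tDCS has done nothing

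*Combined protocol and SAP*

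**What the plan says.** **The buzz is set once, before the task.** Sections 8.9 (item 3) and 12.3 raise the voltage until the subject rates it 7 out of 10 for annoyance. Section 12.3 then records that the "settings will be set at this voltage".

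**It can be lowered, or the task ended, later.** Section 12.2: "The patient may stop at any time or have the stimulus reduced at any time". Section 12.3 adds that subjects "they may also elect to terminate testing at any time".

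**Current rises within a visit.** Section 8.9 (item 3): "the subject will complete 4-6 trials during which tDCS will be administered at gradually increasing electrical doses during 50% of the trials". The remaining trials are off or sham and serve as baseline. Neither their order nor their voltage relative to the tDCS trials is stated.

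**Scoring.** Section 8.25, Hypothesis 2a: "If there is a statistically significant difference between the two conditions during treatment it will be assumed that suppression did not occur". The interim rule in 13.2 is worded differently and asks for significant inhibition of the pupil response.

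**Use of the score.** It feeds the 8/10 Go criterion (8.25) and the lowest tolerated dose that suppresses the response (8.4, Last 10 Subjects). In 8.4 (R33 Phase) a team member without subject contact computes the response in the 5 minutes between treatments and tells the treating physician whether to go on or stop.

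**Data exclusion.** The only rule is removal of pupil artefacts (8.9, item 1).

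**The concern.** The right to lower the buzz or stop is not in question. The fault is that the score takes no account of it. A weaker buzz should reduce the pupil difference between the paired and unpaired tones, and fewer tones reduce the power to detect it. Under the 8.25 rule both make non-significance more likely, and non-significance is read as success. No section requires the voltage or the tone count to be logged per trial, sets a minimum tone count, or asks for a comparator at the same voltage. Nothing obliges staff to tell the person computing the response that the buzz was changed.

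What is at stake first is the subject's personalised level. One altered trial can end titration at a level that did not suppress anything, and that level is carried into the CO₂ session. R21 titration outcomes also supply the distribution of sham stop levels for the R33 control arm (8.4). The cohort-level Go count is a secondary exposure.

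**Working it through.** **The plan's own figures, reproduced.** 20 high + 20 low = 40 tones per trial. 20 paired tones × 50% = 10 buzzes. 4 to 6 trials × 50% = 2 to 3 tDCS trials per visit. 80% of 10 = 8/10. All agree with 8.9, 8.25 and 13.2. The documents state no power or effect size for the single-subject suppression test, so what follows is an illustration.

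**Assumptions not in the documents.** tDCS is inert; two-sided 5% test; independent tone epochs; full-strength, full-length power of 90% (range 80% to 99%); pupil difference proportional to rated annoyance, so level 5 gives 5/7 and level 4 gives 4/7 of the full effect.

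**Formula.** With n tones per condition and standardised difference d, T is noncentral t with 2n − 2 degrees of freedom and noncentrality d√(n/2). The chance of a false suppressed call is P(|T| ≤ critical value).

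**Base case.** n = 20, critical value 2.024. Power of 90% needs d = 1.05, noncentrality 3.33.

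- Level 7, full trial: 10% scored suppressed.
- Level 5: d = 1.05 × 5/7 = 0.75, noncentrality 2.38: **36%**.
- Level 4: d = 1.05 × 4/7 = 0.60, noncentrality 1.90: **54%**.
- Level 7, half the tones: n = 10, critical value 2.101, noncentrality 1.05 × √5 = 2.35: **40%**.

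**Range over assumed full-trial power.**

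| Full-trial power | Level 7 | Level 5 | Level 4 | Half the tones |
|---|---|---|---|---|
| 80% | 20% | 48% | 64% | 51% |
| 90% | 10% | 36% | 54% | 40% |
| 95% | 5% | 27% | 46% | 30% |
| 99% | 1% | 14% | 31% | 16% |

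**Effect on the 8/10 count.** Take 90% power, one scored tDCS trial per subject, and a harsher case in which the response is halved (noncentrality 1.66, false call 63%). If a share s of subjects is affected, p = (1 − s) × 0.10 + s × 0.632, and the Go chance is P(Binomial(10, p) ≥ 8).

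- s = 30%: p = 0.260, Go chance 0.0006.
- s = 50%: p = 0.366, Go chance 0.007.
- s = 100%: p = 0.632, Go chance 0.23.

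If any one of three tDCS trials may count and only the third is affected, an unaffected subject has p = 1 − 0.9³ = 0.271 and an affected one has p = 1 − 0.9² × 0.368 = 0.702. The Go chance is then 0.0008 with nobody affected, 0.046 with half affected (p = 0.487), and 0.39 with all affected.

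**The two suppression criteria.** Under 8.25, a weaker buzz and a shorter trial both push towards suppressed. Under the 13.2 wording, a weaker buzz still does so if the comparison trial had the full buzz. A shorter trial mostly loses power to show inhibition, so its error runs the other way. The short-trial part of the point therefore rests on 8.25 alone.

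**The case against.** **The root fault is the rule that non-significance means suppression.** This stands. Section 8.9 already collects same-visit off/sham trials, and a direct comparison with them would cure most of the problem. It would not cure all of it: a tDCS trial at a lowered buzz compared with an off trial at full buzz still favours tDCS, so matching on voltage is needed as well.

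**Only some of the trial is exposed.** This stands. The plan allows the Anxiety Task or the Auditory Oddball Test throughout, Aim 3 (8.3) names only the oddball task for dose choice, and that task has no buzz.

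**Stronger readings that the documents do not support:**

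- A reader might infer that every altered trial is scored as suppressed. The documents support only that it can be, when the difference loses significance. They give no rate of reductions or stops, and do not say whether a stopped trial is scored.
- A reader might infer that requests to lower the buzz will cluster at the higher currents because scalp discomfort adds to it. No section says so, and the tolerability rules (8.9, item 2; 13.2) remove subjects rating tDCS discomfort above mild. The documents show only that current ascends, so a reduction carried forward would fall on higher currents.
- A reader might take the 25% pupil non-response rate in 8.4 and 10.1 as evidence of 75% test power. It is a between-subject screening failure rate, and enrolled subjects have already shown a significant response (10.7, criterion 4).

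**The pain-triggered reduction in 12.2 follows the calibration text.** True, but the quoted permission has no such limit, and 12.3 allows testing to be ended at any time.

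**Conclusion.** The point holds for the Anxiety Task. As written, a tDCS trial at a lowered buzz, or under 8.25 a shortened one, can be called suppressed without any tDCS effect. Given 90% full-trial power and a response proportional to annoyance, the chance per affected trial goes from 10% to between 36% and 54%. With half the tones it is 40%. How often this happens cannot be judged from the documents.

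The practical risk is a wrong personalised level for a single subject. A reader might infer that the Go decision itself is unsafe. The figures do not support that unless most subjects are affected and their response falls sharply.

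The finger site is a separate, editorial inconsistency. Section 8.9 has the buzz "presented through stimulation generated to the index and middle fingers of the subject", while 12.3, describing the same calibration, has it "presented through stimulation generated to the ring and pinky fingers of the subject". Nothing suggests that the site changes between trials, so it adds nothing to the bias argument.

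**What to change.** In 8.9 and 8.25:

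1. Log the voltage and the number of tones delivered for every trial, and pass both to the team member who computes the response.
2. Score a tDCS trial by direct comparison with off/sham trials of the same visit run at the same voltage.
3. Treat as not evaluable any trial in which the buzz was lowered or that was cut short, and any later tDCS trial with no off/sham trial at its voltage. Such a trial cannot count as suppressed or fix the level.
4. Count a subject left with no evaluable suppressed trial as not suppressed in the 8/10.
5. Reconcile the suppression criteria in 8.25 and 13.2, and separately the finger site in 8.9 and 12.3.

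**Cost.** Protocol and SAP wording, two logged fields, and somewhat fewer evaluable trials. No extra trial is asked for. Six 12-minute trials with five 5-minute breaks already take 72 + 25 = 97 minutes, against 90 minutes for a later visit in 11.13. An added off trial after tDCS could also be blunted by carry-over, which 8.4 anticipates by mapping persistent effects. The subject's right to reduce the buzz or stop is unchanged.
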